7.4.8. MRI sub-study assessments

Each of the 51 participants recruited into the MRI sub-study (17 from each arm of the study in the North East of England) will undergo two MRI scans of their temporomandibular joints, and temporalis and masseter muscles. The first scan will take place between trial visit 1 and visit 2 (day -28 to -1) and must be prior to commencement of trial intervention, where possible. The second MRI visit will occur within +/- 7 days of the week 36 visit. MRI scans will take place at the Centre for In Vivo Imaging, Newcastle University. Each MRI scan will take approximately 1 hour. If for any reason an MRI scan is of insufficient quality for research assessments, if appropriate, a repeat scan may be arranged with the participant's consent.

Any incidental findings during the MRI procedure will be identified by the radiologist reviewing the scan, who will report to the Newcastle clinical team, who will contact the patient to discuss the finding and inform the local site team and GP/Dentist/Consultant as appropriate. Further monitoring, investigation, or treatment, as appropriate, would then be conducted in the usual NHS care pathways for the finding identified. If the finding clearly and unambiguously nullifies the M-TMD diagnosis or meets another exclusion criteria, the patient would be withdrawn from the trial and informed of this whilst discussing the finding with the clinical team. Otherwise, as long as the patient was happy to continue in the trial, this would be possible.

A venous blood sample totalling approximately 4 – 6 mL in an EDTA tube will be taken at each of the two MRI visits. Each sample will be used to measure serum biomarkers of bone turnover CTX and P1NP at screening and at 36 weeks. Samples will be labelled in accordance with the Sponsor's usual requirements and will be transported, stored, accessed, and processed in accordance with national legislation relating to the use and storage of human tissue for research purposes and such activities shall at least meet the requirements as set out in the 2004 Human Tissue Act. Once blood samples have been analysed, they will be disposed of in accordance with local site protocols. Analysis will take place in the Sponsor's clinical laboratories (Newcastle Laboratories) or via Newcastle Laboratories as part of a service level agreement with an external laboratory in compliance with the UK Data Protection Act 2018, the UK GDPR as amended on 01 January 2021 by regulations under the European Union (Withdrawal) Act 2018, and the 2004 Human Tissue Act. If it is not possible to perform analysis on the blood sample for any reason (e.g., degraded sample, insufficient sample), if appropriate, a repeat sample will be obtained with the participant's consent.

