7.1.5. Randomisation

Those who provide informed consent and fulfil eligibility criteria will be randomly allocated stratified by psychosocial status (PHQ-4 score≥6 (Penlington et al., 2020)) and site in a ratio of 1:1:1 to one of the three arms of the study: TAU, lidocaine injections, or Botulinum toxin type A injections 3 monthly for 3 cycles (weeks 0, 12, 24). The randomisation process will use the Sealed Envelope (SE) system (a central, secure, 24-hour web-based randomisation system with concealed allocation). The SE system will use random permuted blocks within strata. Those who have been delegated the randomisation task at local sites will be provided with personal login IDs and passwords. The study is open label. Those participating in the trial north-east of England (Newcastle, Sunderland, Middlesbrough sites) will be offered the opportunity to participate in the optional MRI sub-study. Seventeen participants from each arm of the trial will be sequentially selected from those who opt-in to the sub-study making a total of 51 participants in the sub-study.

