Eligible participants will be randomised at the end of the screening visit (visit 1). A follow up visit (visit 2) will be scheduled following randomisation to start treatment for those participants randomised to Botox or lidocaine. This should ideally be within 14 days of screening but may be up to 28 days. Administration of IMP may occur on the same date as the screening visit, following randomisation, should the participant and investigator both agree to this.

For participants randomised to TAU, they may receive a prescription to obtain their medication at the screening visit, or their GP will be contacted to ask them to prescribe it. For those participants who agree to undergo an MRI, the participant should be advised not to start their medication until after the completion of the MRI, if possible.

7.4.3. Visit 2 – Day 0

Participants will commence treatment at visit 2. For those randomised to receive an injectable, this will be their first cycle of treatment. For those participants allocated to TAU, this will be the start date of their medication, but does not need to be an in-person visit. The start date of the medication will be reported on ePro by the participant or reported to the trial team by telephone who will record this date in the eCRF. Further visit dates will be calculated from this Day 0 timepoint.

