10. STATISTICAL CONSIDERATIONS

10.1. Analysis Populations

Intention-to-treat (ITT): This population contains all participants randomised into the trial who participated in at least one post-baseline assessment, analysed according to randomised treatment allocation.

Safety Population (SP): This population contains all participants who received **any** trial treatment, analysed according to randomised treatment allocation.

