10.2. Statistical Analyses

The analysis of all outcome measures will be described in detail in a pre-specified Statistical Analysis Plan (SAP) that will be reviewed by the trial's oversight committees and signed off by the CI prior to any comparative analyses being undertaken. Any changes to the statistical analysis plan made afterwards will be documented and reviewed by the senior methodological lead who has not had access to the results of the comparative analyses. Throughout the statistical section (section 10.2), baseline refers to data collected before randomisation at the screening visit.

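### Section 7.4.8 withdraws participants from the trial on an MRI taken after randomisation; those withdrawn on the first scan give no follow-up outcome and leave the ITT set

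*Protocol*

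**What the plan says.** **Order of events.** Protocol section 7.4.2 places allocation at the end of visit 1: "Eligible participants will be randomised at the end of the screening visit (visit 1)". Section 7.1.5 fills the MRI sub-study by arm: "Seventeen participants from each arm of the trial will be sequentially selected from those who opt-in to the sub-study", 51 in all, from the north-east sites. Section 7.4.8 then times the scans: "The first scan will take place between trial visit 1 and visit 2 (day -28 to -1)" and "The second MRI visit will occur within +/- 7 days of the week 36 visit".

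**The rule.** For an incidental finding, section 7.4.8 states: "If the finding clearly and unambiguously nullifies the M-TMD diagnosis or meets another exclusion criteria, the patient would be withdrawn from the trial". The sentence after it lets everyone else stay if they wish, so in this branch withdrawal is the set consequence, and it is from the trial rather than from treatment or from the sub-study.

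**The analysis set.** Section 10.1 defines ITT as "all participants randomised into the trial who participated in at least one post-baseline assessment", and section 10.2.1 runs the co-primary analysis in that population.

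**The rest of the protocol.** Section 7.5 says that stopping treatment does not oblige anyone to leave the trial, and asks for the week-36 assessments as a minimum. Its own list of withdrawal reasons is permissive. Section 7.6 continues the scheduled assessments after treatment stops, apart from the MRI sub-study. Section 10.2.1 sets a treatment-policy estimand for treatment deviations and for new treatments.

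**The concern.** Main-trial eligibility rests on a clinical diagnosis derived from the DC/TMD criteria and needs no MRI. The rule therefore gives a second eligibility screen to the scanned participants alone, after allocation, in a trial where the clinical team knows the arm. A primary analysis that is meant to follow everyone as randomised should not lose people because eligibility was judged again later.

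At stake is the integrity of the randomised comparison more than precision. Section 7.5 keeps data collected up to withdrawal, but that does not help someone withdrawn on the first scan, because no follow-up outcome exists yet. Nor can the analysis plan recover outcomes that the protocol has stopped collecting.

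**Working it through.** **1. What is lost, by time of withdrawal**

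| Withdrawn after | Follow-up CPI and OHIP-TMD held | In the ITT set (10.1)? |
|---|---|---|
| First scan, before week 12 | none | no |
| Week 12, before week 24 | week 12 | yes |
| Week 24, before the week-36 questionnaires | weeks 12 and 24 | yes |
| Week-36 questionnaires completed | all | yes |

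The table assumes that the earlier assessments were completed. Loss from the ITT set is thus essentially a first-scan matter. Later withdrawals keep their earlier values, and the mixed model in 10.2.1 uses all timepoints.

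One qualification: section 10.2 says that "baseline refers to data collected before randomisation at the screening visit". Read literally, the first scan could then count as post-baseline and keep the person in the ITT set by name. Section 7.4.8, however, treats the blood markers taken at that visit as screening values. On either reading, no follow-up CPI or OHIP-TMD reaches the model.

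**2. The plan's own sample size (10.3), reproduced first**

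Inputs: SD 20.7, difference 6.0, correlation with baseline 0.6, two-sided 5%, power 90%, loss 27%.

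- Unadjusted: 2 × (1.960 + 1.2816)² × 20.7² / 6.0² = 250.1, so 251 per arm.
- Adjusted for baseline: (1 − 0.6²) × 251 = 160.6, so 161 per arm.
- Inflated for loss: 161 / 0.73 = 220.5, so 221 per arm.
- Total: 3 × 221 = 663, which matches.

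**3. How many are exposed**

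51 / 663 = 7.7% overall; 17 / 221 = 7.7% of each arm.

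**4. Effect on power for OHIP-TMD**

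The protocol gives no rate of disqualifying findings, so the rate r is an assumption. The adjusted SD is 20.7 × √(1 − 0.36) = 16.56. Evaluable per arm is m = (221 − 17r) × 0.73, and power is Φ(6 / (16.56 × √(2/m)) − 1.96). As an upper bound on the loss, every finding is taken to act at the first scan.

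| r | Removed (51r) | Share of 663 | m per arm | Power |
|---|---|---|---|---|
| 0 | 0 | 0% | 161.3 | 90.2% |
| 1% | 0.5 | 0.1% | 161.2 | 90.2% |
| 5% | 2.6 | 0.4% | 160.7 | 90.1% |
| 10% | 5.1 | 0.8% | 160.1 | 90.0% |
| 100% (extreme) | 51 | 7.7% | 148.9 | 87.8% |

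**The case against.** The strongest reply is that the rule is narrow and nearly harmless. A radiologist identifies the findings, the threshold is high, and the scanned group is balanced at 17 per arm. The first scan is planned before treatment where possible, so what it shows should be almost unrelated to arm. Power hardly moves. The exit from the ITT set comes from the definition in 10.1, which treats anyone who withdraws before week 12 in the same way. All of this stands, and it limits the size of the point. It does not remove it: 7.4.8 makes exit the set consequence for people who could have been followed, while 7.5 and 7.6 follow people who stop treatment.

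It can also be said that keeping such people would amount to an eligibility waiver. Section 6 forbids enrolling patients who do not meet the criteria. These participants were assessed as eligible before randomisation, and continuing to collect their outcomes is not enrolment.

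Three stronger readings are tempting, and the protocol does not support them:

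- **That the week-36 scan also removes people from the ITT set.** By then they normally hold week-12 or week-24 data and remain in it. The scan may fall up to 7 days before the visit, so losing the week-36 co-primaries is possible. But the questionnaires may themselves be collected up to 7 days ahead, and the scan must first be read and reported.
- **That a structural joint change, itself a sub-study outcome, would trigger withdrawal.** Sections 4 and 6.2 allow comorbid TMD, even painful, provided that it is not the primary cause of the familiar pain. Such a change would not ordinarily meet the rule.
- **That the rule biases the comparison between arms.** Staff know the allocation, so findings could be acted on differently by arm, but nothing in the protocol shows that they would be. Confinement to a few sites does not in itself bias a comparison stratified by site.

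**Conclusion.** The point holds within limits. Section 7.4.8 creates an avoidable post-randomisation exclusion in an open-label trial. It conflicts with the treatment-policy aim of 10.2.1 and with the follow-up principle of 7.5 and 7.6. Its full effect, with no follow-up outcome and loss from the ITT set, applies to withdrawal on the first scan; later withdrawal costs only the remaining outcomes.

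The likely effect on the co-primary results is small: about 0.5 to 5 of 663 participants, with power at 90.0% to 90.2%. This rests on the assumed 1% to 10% rate of disqualifying findings and on the plan's own SD, correlation and 27% loss. The case for change is that the exclusion is unnecessary and cheap to avoid, not that it threatens the trial's conclusion.

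**What to change.** Reconcile 7.4.8 with 7.5, 7.6 and 10.1. State that, whatever clinical decision follows the finding, a randomised participant is asked to continue the scheduled CPI and OHIP-TMD assessments, with week 36 as a minimum, and is analysed in the ITT population in the allocated arm. How the finding is handled clinically stays with the investigators and is not part of this change.

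Add a sensitivity analysis that leaves out participants judged not to have M-TMD. The judgement should be made from the pre-treatment scan only, by someone unaware of the arm.

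Make no change to the second-scan rule. Section 7.6 already ends MRI assessments once treatment stops, and a finding may be one of the MRI contraindications in exclusion criterion 18.

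The cost is a short edit at the next protocol amendment and a line in the SAP. No sample-size figure changes. The downside is that a few participants without true M-TMD stay in the ITT analysis and dilute the effect very slightly; the sensitivity analysis would show by how much.

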7.4.9. Qualitative evaluation

A qualitative evaluation will explore barriers and facilitators to study participation and trial progress with those sampled at the screening visit. Thereafter an embedded piece of longitudinal qualitative research will explore participants' perspectives of the treatment received.

Participants will be recruited from all treatment arms, including those who withdraw or choose not to participate despite meeting eligibility criteria (apart from agreeing to consent to the trial). Up to 30 participants will be recruited for semi-structured interviews across all sites in the pilot. Up to 20 of these participants will then go on to have sequential interviews at 12 and 24 or 36 weeks to explore treatment experiences. Interviews will be conducted by a trained interviewer from the research team over Zoom; however, a contingency will be available for participants who may not have access to Zoom to ensure a diverse range of participants will be included. This may include either Microsoft Teams, a telephone or face-to-face interview. Live interpretation will be possible for non-English speakers. Recruitment will be via purposive, maximum variation sampling stratified by age band, sex, decile of index of multiple deprivation and ethnic group to ensure a diverse range of participants are included. A summary table of pseudonymised characteristics from the research database will be provided by NCTU to the qualitative team for the purpose of sample selection for the qualitative research.

Recruitment and analysis will follow the principles of the constant comparative method (Glaser, 1965), occurring concurrently until data saturation is achieved. Interviews will be informed by interview topic guides, which will be collaboratively constructed with PPIE input, and reviewed and refined as data collection and analysis progresses.

7.4.10. Schedule of Events

		Day -28 to -1ª (Visit 1)	Day 0 (Visit 2)	Week 12 (Visit 3) +/- 7 days	Week 24 (Visit 4) +/- 7 days	Week 36 (Visit 5) ^c +/- 7 days	Week 37 (+3 days)	Unscheduled Visit - Facial Weakness, medication concern, or other
Activity	Identification potential participants	Face-to-face screening	1 st dose of IMP ^a	Research Assessment IMP review and/ or provision ^b	Research Assessment IMP review and/ or provision ^b	Research Assessment	Phone call	Research Assessment (As/If required)
	Potential participant identification							
Clinical team providing care review clinical notes or databases	х							
Self-referring individual self- screens and makes email contact ¹	х							
Provide PIS +/- invitation letter/email as appropriate	Х							
	Consent & eligibility							
Informed Consent		х		X ^d	X ^d	x ^d		
Dipstick pregnancy Test		х				x ^e		
Confirmation of eligibility		x						
	Routine Data Collection ²							
Sociodemographics		x						
PMH (systems, meds, allergies, daily analgesia use, non-drug therapies)		х						
Medical review (systems, con meds, allergies, daily analgesia use, non-drug therapies)				х	х	х		
Clinical examination inc CN V & VII		X		х	x	х		
Blood pressure, Pulse, Weight, & Height. Height only at day screening		х		х	х	х		
Diagnosis & TMD history		Х						
ID-Migraine +/- Migraine history & MIDAS ²		x		x ^f	x ^f	χ ^f		
	Research assessments (occur prior to		tration or review of					
Pain reporting assessment & feedback		х		Х				

		Day -28 to -1 ^a (Visit 1)	Day 0 (Visit 2)	Week 12 (Visit 3) +/- 7 days	Week 24 (Visit 4) +/- 7 days	Week 36 (Visit 5) c +/- 7 days	Week 37 (+3 days)	Unscheduled Visit - Facial Weakness, medication concern, or other
Activity	Identification potential participants	Face-to-face screening	1 st dose of IMP ^a	Research Assessment IMP review and/ or provision ^b	Research Assessment IMP review and/ or provision ^b	Research Assessment	Phone call	Research Assessment (As/If required)
PHQ-4 & red flag assessment		x		х	Х	х		
GCPS		х						
CPI (within GCPS ³)		x		х	х	Х		
OHIP-TMDs		x		х	х	Х		
EQ-5D-5L		х		х	х	Х		
BPSQI		х		х	х	Х		
SF-JFLS		х		х	х	Х		
GIC				х	х	Х		
LAEP				х	х	Х		
FaCE scale and facial				Optio	onal, as determined by	patient		х
weakness exam								
AE & SAE Reporting		х	х	х	х	Х	x ^g	х
HUQ		х		х		Х		
T&TQ					х			
MRI sub-study assessments: MRI & bone biomarkers ⁴		x (prior to IMP – TAU IMP may be started prior to MRI if it is not possible to delay)				x		
Qualitative interviews		xh (inc declines)		х	Either 24 or 36	weeks not both		
purposive subsample								
	Randomisation		T	ı	1			
Randomisation – after all questionnaires & main study research assessments		Х						
	Treatment							
Dosage schedule (dose and tapers) prescribed or reviewed for TAU arm		X _i	Xi	х	х	Xį		
Botox injections (Botox arm only)			х	х	х			
Lidocaine injections (Lidocaine arm only)			х	х	х			

		Day -28 to -1ª (Visit 1)	Day 0 (Visit 2)	Week 12 (Visit 3) +/- 7 days	Week 24 (Visit 4) +/- 7 days	Week 36 (Visit 5) ^c +/- 7 days	Week 37 (+3 days)	Unscheduled Visit - Facial Weakness, medication concern, or other
Activity	Identification potential participants	Face-to-face screening	1 st dose of IMP ^a	Research Assessment IMP review and/ or provision ^b	Research Assessment IMP review and/ or provision ^b	Research Assessment	Phone call	Research Assessment (As/If required)
1 Solf coroons by shocking solf	assessment questions on duration and M	A TMD (section 7.1.2) on the	a Ideally IMP should	he provided within 14	days of the screening	aither proscription receiv	and or injectable	delivered) but this can be un

¹ Self-screens by checking self-assessment questions on duration and M-TMD (section 7.1.3) on the advert, and then emails clinical study team who send PIS and invitation letter requesting a telephone call. Telephone call to explain study and confirm demographics and TMD status including treatment. Individual then enters study as normal via screening visit at site local to them with GP and GDP informed if screens as eligible and gives consent to participate.

² If ID-Migraine positive then migraine history and MIDAS are completed and updated at that visit and at each subsequent visit, but ID-Migraine is not.

³ CPI forms part of Graded Chronic Pain scale which will be completed at screening in full, following this CPI will be completed on its own at all other visits

⁴ Only for subsample in North-East England (section 7.4.7)

^a Ideally IMP should be provided within 14 days of the screening (either prescription received or injectable delivered), but this can be up to 28 days from screening. If >28 days, it should be recorded as a protocol deviation. IMP administration may also occur on the same date as screening following randomisation if the participant and investigator wish to start then.

^b All research assessments will be collected up to 7 days ahead of any IMP administration at these visits and prior to administration of any further IMP. New local prescriptions will be issued by the GP following instruction from the site teams at weeks 12 and week 24, or by sites for their pharmacy at 12 weeks and at 24 weeks for the patient to collect in the TAU arm.

^c All research assessments will be collected up to 7 days ahead of any IMP administration at these visits and the CRF updated at the visit.

^d Confirmed in writing in the clinical notes at each study visit.

^e Pregnancy test required at 36 weeks for all participants of childbearing potential or 7 days after this point if participants are still on TAU week 36^e

fMigraine history and MIDAS only repeated if positive at any of the previous visits. If reporting a new headache then ID-Migraine, migraine history and MIDAS are completed at that visit and the migraine history and MIDAS are repeated at subsequent visits.

§ Phone call to collect AE data in 7 days since week 36 visit. Only required if participant still receiving TAU IMP at week 36 or stopped IMP after week 35.

^h Qualitative interview will ideally take place during screening but may be up to 4 weeks after consent to the interview. This may be after the start of the IMP in some cases.

TAU prescription may be issued at any point during screening or at Day 0 as appropriate. Day 0 is the first dose of IMP.

Review of medication only at week 36

IMPORTANT: If participants who discontinue trial treatment plan to begin a new therapy for TMD (NHS or private) within the remainder of the trial monitoring period, they should be asked if they will complete the next set of research assessments prior to beginning a new treatment in routine clinical care and then go back on schedule to the next scheduled set of research assessments following this.

Key
AE & SAE - Adverse Event & Serious Adverse Event
BPSQI - Brief Pittsburgh Sleep Quality Index
CN V & VII - 5th Cranial Nerve and 7th Cranial Nerve
CPI (within GCPS) - Characteristic Pain Intensity (Graded Chronic
Pain Scale)
EQ-5D-5L - See section 7.4.6.4
FaCE - Facial Clinimetric Evaluation
GIC - Global impression of change

HUQ – Health Utilisation Questionnaire
MIDAS – Migraine Disability Assessment Test
LAEP - Liverpool adverse events profile
OHIP-TMDs - Oral Health Impact profile for TMD
PHQ-4 - Patient Health Questionnaire-4
PMH – Past Medical History

SF-JFLS - Short-form jaw functional limitation scale

T&TQ – Time and travel questionnaire

10566 MiTiGate Protocol V5.0 07 Oct 2025 Based on NCTU CTIMP Protocol Template version 4.0

Page **43** of **79**

